## Using Triamcinolone Acetonide to Reduce Pain after Scleral Buckle Surgery

Endocrine: Abnormal fat deposits, decreased carbohydrate tolerance, development of Cushingoid state, hirsutism, manifestations of latent diabetes mellitus and increased requirements for insulin or oral hypoglycemic agents in diabetics, menstrual irregularities, moon facies, secondary adrenocortical and pituitary unresponsiveness (particularly in times of stress, as in trauma, surgery or illness), suppression of growth in children

Fluid and Electrolyte Disturbances: Potassium loss, hypokalemic alkalosis, sodium retention

Gastrointestinal: Abdominal distention, elevation in serum liver enzymes levels (usually reversible upon discontinuation), hepatomegaly, hiccups, malaise, nausea, pancreatitis, peptic ulcer with possible perforation and hemorrhage, ulcerative esophagitis

Metabolic: Negative nitrogen balance due to protein catabolism

Musculoskeletal: Aseptic necrosis of femoral and humeral heads, charcot-like arthropathy, loss of muscle mass, muscle weakness, osteoporosis, pathologic fracture of long bones, steroid myopathy, tendon rupture, vertebral compression fractures

Neurological: Arachnoiditis, convulsions, depression, emotional instability, euphoria, headache, increased intracranial pressure with papilledema (pseudo-tumor cerebri) usually following discontinuation of treatment, insomnia, meningitis, neuritis, neuropathy, paraparesis/paraplegia, paresthesia, sensory disturbances, vertigo

Reproductive: Alteration in motility and number of spermatozoa.

- *Privacy (e.g., potential for personal information being accessed, used, or disclosed without the subjects' knowledge or consent, breach of confidentiality/security)*
- In any clinical trial, there is a possibility for patient's personal information being accessed improperly. This has been minimized as much as possible through participation in CITI training by main investigators, as well as not extracting patient identifying information from the EHR for analysis purposes.
- *Economic (e.g., potential for individuals to lose access to economic services, employment, insurability)*
- There will be no additional charge for TA treatment to the patient.

17.2 *If applicable, indicate which procedures might have risks to the subjects that are currently unforeseeable. This will be rare, and usually applicable when testing a new drug or device or a new use of an existing drug or device.*

TA is a very well-studied drug that has been FDA approved since 1957 for ophthalmic application. It is unlikely there will be risks associated with the drug that have not been previously documented.

*17.3 If applicable, indicate which procedures might have risks to an embryo or fetus should the subject be or become pregnant.*

Triamcinolone is Pregnancy Category D, as it has been shown to increase rate of cleft lip in the first trimester when used systemically. It is unlikely to have this effect when applied locally to the eye, but some risk exists nonetheless.

*17.4 If applicable, describe risks to others who are not subjects (e.g., collection of sensitive health data that might affect sexual partners if disclosed, mandatory reporting of abuse, DNA testing that might affect family members or relationships).*

N/A

## **18.0 Potential Benefits to Subjects**

*18.1 Describe the potential benefits that individual subjects might experience from participating in the research. Include the probability, magnitude, and duration of the potential benefits, as this will be useful to the IRB's risk:benefit analysis. Do not include benefits to society or others. These should be included in section 2 or 3 of this document.*

The largest benefit to subjects is the possibility to directly reduce pain following scleral buckle surgery. This is our primary outcome so the exact likelihood and magnitude are currently unknown, but likelihood is presumed to be high based on background literature. Magnitude is presumed to be around 50% reduction in pain. Subjects may also experience a decrease in intraocular inflammation, and post-operative nausea and vomiting. Furthermore, patients may have a reduced risk for addiction to pain medication, as we hope to demonstrate a reduced need for post-operative analgesics following surgery. All patients in the experimental group will also be receiving the treatment at no additional cost to them, which is a potential financial benefit.

## **19.0 Data Management and Confidentiality**

*19.1 Describe procedures that you will use for quality control to ensure validity of collected data.*

The surgeon will be including their subjective assessment of patient's pain on the EHR, which they may compare to the patients written assessment as a form of quality control.

*19.2 Describe the steps that you will take to handle and secure study data during data collection, storage, use, and transmission. Include information about training of study staff, authorization of access,*

*password protection, encryption, physical controls, certificates of confidentiality, separation of identifiers and data, etc.*

Patient data is stored securely in NextGen Electronic Medical Record at Vistar Eye Center according to HIPAA regulations. Data that will be extracted from the EMR will not contain any patient identifying information. The procedure by which it will be extracted is via CPT code records for scleral buckle surgery. De-identified data extracted will be stored in a dataset along with arbitrary patient ID within the Vistar Eye Center computer network so that it cannot be accessed without both physical access and log-in credentials. Access to study materials is granted only to 2 surgeons listed on this document ([name], [name]), and the research coordinator ([name]).

- 19.3 *For multi-site studies, describe how data or specimens will be handled and secured for each site (e.g., central or disseminated data storage, data coordinating center).*
- 19.4 *Describe the plan for data disposition following the conclusion of the study (e.g., long term maintenance of data, data destruction methods).*

Data will not be stored outside of that needed for medical care after the conclusion of the study. Medical information will continue to exist on the Electronic Medical Records at Vistar Eye Center, but all extracted data will be destroyed 3 years following publication of the results of this study as is standard protocol.

- *What information will be included in the long term storage of data or specimens?*
- *How long will the data or specimens be stored?*
- *Where and how data or specimens will be stored?*
- *Who will have access to the data or specimens during long term storage?*
- *Who is responsible for receipt or transmission of the data or specimens?*
- *How will data or specimens be shared or transported?*
- *When and how will personal identifiers be destroyed?*

## 20.0 Provisions to Protect the Privacy Interests of Subjects

- 20.1 *Describe the steps that you will take to protect subjects' privacy interests. "Privacy interest" refers to a person's desire to place limits on with whom they interact or to whom they provide personal information (e.g., collecting the minimal amount of private information required to complete the study, protecting the data once it is obtained).*

No patient identifying information will be extracted from the electronic medical records. The only people with access to this information is the medical care team of the patient. De-identified data will not be shared

beyond the two surgeons involved in the study design and research coordinator.

20.2 *Describe steps that you will take to make subjects feel at ease with the research situation in terms of the questions being asked and the procedures being performed. “At ease” does not refer to physical discomfort, but the sense of intrusiveness a subject might experience in response to questions, examinations, and procedures (e.g., use of a same gender investigator to place sensors on the torso, a private changing area if clothing must be changed, sensitivity when discussing pregnancy testing with subjects, making it clear on surveys that participants can discontinue at any time, not asking questions about private or sensitive issues unless necessary for the research).*

20.3 *Describe how you plan to access existing sources of information about the subjects (e.g., medical records, grades) and how you will protect participant privacy through the data security plan.*

Data extraction from the medical record will be done by one of the two surgeon members of the Vistar Eye Center team who would otherwise have access to the medical data anyway for patient care. The procedure by which it will be extracted is via CPT code records for scleral buckle surgery. De-identified data extracted will be stored in a dataset along with arbitrary patient ID within the Vistar Eye Center computer network.

20.4 *Describe any required reporting that might occur as a result of your research questions, study populations, and data collection methods. Examples for Virginia and Virginia Tech include:*

- *Any suspicions (e.g., circumstantial, disclosed) of child abuse (physical, emotional, sexual) and neglect*
- *Sexual discrimination and/or sexual violence that involves a student*
- *Disclosure or signs of intention to harm oneself (i.e., suicidal ideation and/or plan)*
- *Disclosure or signs of desire to harm others (i.e., homicidal ideation and/or plan)*
- *Suspected abuse, neglect or exploitation of vulnerable adults (e.g., individuals with a disability, elderly persons)*

## 21.0 Provisions to Monitor the Data to Ensure the Safety of Subjects

*Safety monitoring is required when research involves greater than minimal risk and is sometimes appropriate for other studies.*

### 21.1 Describe:

- *The plan to periodically evaluate the data collected regarding both harms and benefits to determine whether subjects remain safe (e.g., periodic reporting to the IRB, establishing a data monitoring*

*committee, reporting data monitoring committee findings to the IRB and the sponsor).*

The patient's IOP will be measured at baseline prior to the surgery, as well as 24 hrs post-op and 2 weeks post-op. This is done to monitor ocular hypertension, a potential side-effect of both the surgery and TA treatment. Patients will also have two normally scheduled follow-up visits with the surgeon who will be monitoring for any other adverse events such as hypersensitivity or infection. If adverse events occur that may be related to the intervention, they will be reported to the IRB promptly. The data will also be monitored after every 10th patient completes the protocol for any statistically significant differences in the primary or secondary safety endpoints. If this occurs, it too will be reported to the IRB promptly.

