### 4.2 *Describe any primary or secondary safety endpoints. These should be included for all studies that are greater than minimal risk.*

- Primary: No significant difference in ocular hypertension 1-2 weeks post-operatively, defined as IOP of >5mmHg above baseline
- Secondary:
  - No significant difference in infections following surgery
  - No significant difference in hypersensitivity following surgery

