## 17.0 Risks to Subjects

*17.1 List the reasonably foreseeable risks, discomforts, hazards, or inconveniences to the subjects related to the subjects' participation in the research.*

Adverse event data was collected by the FDA from 300 published articles containing data from controlled and uncontrolled clinical trials which evaluated over 14,000 eyes treated with different concentrations of triamcinolone acetonide. The most common dose administered within these trials was triamcinolone acetonide 40 mg administered as primary or adjunctive therapy primarily as a single injection. The most common reported adverse events following administration of triamcinolone acetonide were elevated intraocular pressure and cataract progression. These events have been reported to occur in 20-60% of patients. Less common reactions occurring in up to 2% include endophthalmitis (infectious and non-infectious), hypopyon, injection site reactions (described as blurring and transient discomfort), glaucoma, vitreous floaters, and detachment of retinal pigment epithelium, optic disc vascular disorder, eye inflammation, conjunctival hemorrhage and visual acuity reduced. Cases of exophthalmos have also been reported.

**Risk of infection:** Corticosteroids may mask some signs of infection, and new infections may appear during their use. There may be decreased resistance and inability to localize infection when corticosteroids are

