## Using Triamcinolone Acetonide to Reduce Pain after Scleral Buckle Surgery

used. Corticosteroids may enhance the establishment of secondary ocular infections due to fungi or viruses. If an infection occurs during corticosteroid therapy, it will be promptly controlled by suitable antimicrobial therapy.

**Elevated Intraocular Pressure:** Increases in intraocular pressure associated with triamcinolone acetonide injection have been observed in 20-60% of patients. This may lead to glaucoma with possible damage to the optic nerve. Effects on intraocular pressure may last up to 6 months following injection and are usually managed by topical glaucoma therapy. A small percentage of patients may require aggressive non-topical treatment. Intraocular pressure as well as perfusion of the optic nerve head will be monitored and managed appropriately. As our study will be irrigating the peribulbar space rather than injecting into the posterior capsule of the eye, we expect our rate of elevated IOP to be much lower than that determined by the FDA.

**Endophthalmitis:** The rate of infectious culture positive endophthalmitis is 0.5%. Proper aseptic techniques will always be used when administering triamcinolone acetonide. In addition, patients will be monitored following the injection to permit early treatment should an infection occur.

**Cataracts:** Use of corticosteroids may produce cataracts, particularly posterior subcapsular cataracts. As our study will be irrigating the subtenon's space rather than injecting into the posterior capsule of the eye, we expect our rate of cataracts to be much lower than that determined by the FDA.

**Patients with Ocular Herpes Simplex:** Corticosteroids should be used cautiously in patients with ocular herpes simplex because of possible corneal perforation. Corticosteroids should not be used in active ocular herpes simplex. We will be excluding all patients with ocular herpes simplex.

Systemic reactions are exceedingly rare in ophthalmic administration of corticosteroids but are included below for completeness:

**Cardiovascular:** Bradycardia, cardiac arrest, cardiac arrhythmias, cardiac enlargement, circulatory collapse, congestive heart failure, fat embolism, hypertrophic cardiomyopathy in premature infants, myocardial rupture following recent myocardial infarction, pulmonary edema, syncope, tachycardia, thromboembolism, thrombophlebitis, vasculitis

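### Arm-level safety looks reach the IRB only on statistical significance, so at 10 to 40 patients they almost never flag infection and usually miss moderate IOP excesses

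*Combined protocol and SAP*

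**What the plan says.** Section 21.1 gives two routes by which safety information reaches the IRB.

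- **Single events:** "If adverse events occur that may be related to the intervention, they will be reported to the IRB promptly". No test or minimum count applies.
- **Arm-level looks:** "The data will also be monitored after every 10 th patient completes the protocol", and the look is made "for any statistically significant differences in the primary or secondary safety endpoints. If this occurs, it too will be reported to the IRB promptly". Nothing says that by-arm counts go to the IRB when the difference is not significant.

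The endpoints compared at these looks are in section 4.2. The primary one is "No significant difference in ocular hypertension 1-2 weeks post-operatively, defined as IOP of >5mmHg above baseline". The secondary ones are infection ("No significant difference in infections following surgery") and hypersensitivity.

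Section 5.2 names tests for pain, analgesic use and nausea and vomiting, but none for safety. The only alpha in the document, 0.01 in section 14.1, belongs to the sample size for pain.

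**The concern.** Looks every 10 patients are there to show harm building up while patients are still being enrolled. A significance test on 5 to 20 patients per arm needs a large imbalance before it responds. If the by-arm comparison is sent on only when that test is positive, a real but moderate excess can build up over several looks with no arm-level report.

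The single-event route does not fill this gap. It depends on a judgement that an event may be related, and it carries no denominators and no matching control-arm count. Under sections 8.1 and 8.2 the surgeon examines for adverse events, and section 8.1 says the surgeon cannot be masked. Attribution is hardest for IOP, because section 21.1 itself names both the surgery and the drug as possible causes of ocular hypertension. That is where a comparison between arms would tell the IRB most.

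This point concerns only what triggers a report at the looks. It does not concern when the looks fall or the final safety conclusion.

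**Working it through.** **Plan's own figures.** The documents give no threshold or operating characteristic for the looks, so there is none to reproduce. The total of 48 does reproduce approximately: d = 2/√((1² + 2.5²)/2) = 1.05, and at two-sided alpha 0.01 a t-test with 24 per arm has power 0.82.

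**Inputs from the documents**
- Looks after every tenth completer (21.1), with N = 48 (1.0): looks at 10, 20, 30 and 40 patients, or about 5, 10, 15 and 20 per arm.
- Coin-flip allocation (8.1), so arms at a look can be unequal.
- Infection: "The rate of infectious culture positive endophthalmitis is 0.5"% (17.1). The same section puts endophthalmitis, infectious or not, among reactions seen in up to 2%.
- IOP: "Increases in intraocular pressure associated with triamcinolone acetonide injection have been observed in 20-60% of patients" (17.1), with this trial's rate expected to be much lower.

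**Assumptions.** Two-sided Fisher exact test at 0.05, with 0.01 also shown for one case. The documents give no control-arm IOP rate, so a range is used.

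**Step 1: smallest significant split against zero events.** With n per arm and x v 0 events, the two-sided p is 2 × C(n,x)/C(2n,x).

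| Patients | Per arm | Not significant | Significant |
|---|---|---|---|
| 10 | 5 | 3 v 0: 2 × 10/120 = 0.167 | 4 v 0: 2 × 5/210 = 0.048 |
| 20 | 10 | 4 v 0: 2 × 210/4845 = 0.087 | 5 v 0: 2 × 252/15504 = 0.033 |
| 30 | 15 | 4 v 0: 0.100 | 5 v 0: 0.042 |
| 40 | 20 | 4 v 0: 0.106 | 5 v 0: 0.047 |

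Control-arm events raise the bar: at 20 per arm it takes 7 v 1 or 9 v 2.

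**Step 2: unequal arms.** With 4 triamcinolone and 6 control patients, 3 v 0 gives C(4,3)/C(10,3) = 4/120 = 0.033. With 8 and 12, 3 v 0 gives 56/1140 = 0.049. With the imbalance reversed, the bar rises to 5 v 0 (6:4) and 6 v 0 (12:8). An uncorrected chi-square test on equal arms needs 3 v 0 at 10 patients and 4 v 0 later.

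**Step 3: chance of a flag at any of the four looks.** Simulated trials with cumulative data, Fisher 0.05.

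| Event rates, triamcinolone v control | Equal arms | Coin-flip arms |
|---|---|---|
| Infection 2% v 0.5% | about 0.01% | – |
| Infection 5% v 0.5% | 0.3% | 0.8% |
| IOP 20% v 10% | 9% | 10–11% |
| IOP 20% v 5% | 18% | – |
| IOP 30% v 10% | 28% | – |
| IOP 40% v 20% | 23% | 27% |
| IOP 40% v 10% | 53–54% | – |
| IOP 60% v 20% | 69% | – |
| IOP 60% v 10% | 92% | – |

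At 40% v 20%, the first two looks together flag 8% of the time. At alpha 0.01 the four looks together flag that case 8% of the time.

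**The case against.** **The IRB is not left blind.** A reader might infer that harm could accumulate without the IRB hearing of it. The documents do not support that. Possibly related events are reported promptly and singly, and "may be" related is a low bar. Section 17.1 itself links corticosteroids to secondary infection, and section 21.1 links IOP rise to the drug. Several infections in the triamcinolone arm would be hard to class as unrelated. Nor do the documents show that the surgeons would attribute events wrongly. What is missing is the comparison by arm, with denominators.

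**The looks are not useless for IOP.** It is tempting to say they miss most plausible IOP harm. That depends on control rates the documents do not give. In the upper part of the quoted 20–60% range, against a low control rate, the looks flag more often than not. The weakness is in moderate excesses, which is where section 17.1's expectation of much lower rates points.

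**Four or five against none is not a strict floor.** No test or alpha is stated, and Step 2 shows that 3 v 0 can be enough. At 20 patients split 8:12, 4 v 0 gives p = 0.014 and would trigger.

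**The 0.5% is not a control-arm rate.** Section 17.1 gives it as a risk of triamcinolone, and only for culture-positive endophthalmitis, while the endpoint covers all infections. Its use for the control arm is an assumption.

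**Low power comes from N = 48, and no trigger changes that.** This stands. Early tables will be imprecise: the exact 95% interval is 0–52% for 0/5 and 0.5–72% for 1/5. But imprecision argues for showing the IRB the counts, not for withholding them until a test is significant. Requiring the IRB to rule on continuation at every look would be a governance choice, and it is not asked for here.

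**Conclusion.** The concern holds in limited form. Significance is the only stated trigger for arm-level reporting. On looks of 10 to 40 patients that makes the comparison nearly silent for infection (under 1% even at an assumed 5% v 0.5%). It is unlikely to flag IOP excesses of 10 to 20 points over an assumed control rate of 10% or more: in the three such cases examined, between about 9% and 28% with equal arms. Large gaps are often flagged.

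The exact figures rest on Fisher's test at 0.05 and on assumed event rates. Coin-flip arms change them by a few points at most in the cases checked, and alpha 0.01 makes the looks weaker. The conclusion about infection does not depend on whether 0.5% or 2% is taken from section 17.1. This is a weakness of the monitoring rule, alongside a single-event route that does work. It does not bear on the pain analysis.

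**What to change.** In section 21.1, replace the significance trigger with a short table sent to the IRB at each 10-patient look. It should give, by arm, the number of events and the number of patients assessed for ocular hypertension, infection and hypersensitivity, with exact confidence intervals, whether or not the arms differ significantly and whatever the attribution of individual events. Keep the prompt reporting of single events as it stands. Any threshold for pausing is for the sponsor and IRB to set; none is proposed here.

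The cost is a wording change and four short tables over the trial, from data already collected. The downsides are small: intervals at the first looks will be wide, and the IRB will see some imbalances that are due to chance.

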## **22.0 Compensation for Research Related Injury**

*22.1 If the research involves more than minimal risk to subjects, describe the available compensation in the event of research-related injury, if any.*

*n/a*

*22.2 Provide a copy of contract language, if any, relevant to compensation for research-related injury. At Virginia Tech, this is most common for sponsored research.*

*n/a*

